### Table 7. Schedule of procedures: Staggered bilateral patients recruited from Cohort 2 into Cohort 2 – All sites (except \* which are UK sites only and \*\* which are online only)

✓ = First Study Hip

✓ = Contralateral Second Hip

 $\sqrt[n]{-1}$  To be taken only if previously DXA scan not done

#### Table 8. Schedule of procedures: Staggered bilateral patients recruited from Cohort 1B into Cohort 2 or vice versa

Col	hort 1B Study Hip	Pre-op	Op day	2D	6 wks	3 mos	6 mos	9 mos					1 year		2 years		3 years			4 years	5 years		6 years	7 years		8,9 years	10 years	
Col	hort 2 Study Hip								Pre-op	Op day	2D	6 wks		6 mos		1 year		2 year	3 year			5 years			7 years			10 years
	Informed consent								~																			
	Inclusions/exclusions								~																			
	Patient registration								~																			
	DXA Scan								√^ ≤12 mos prior																			
	Medical History								 																			
	Operative data									 																		
L	Treadmill gait								 				✓			 					✓	 						
Assessment	Harris Hip Score	Ass	essm	nents	don	e as r	oer Ta	able	 			 	~	 	✓	 	✓	 	√		✓	 		~	 		✓	 
sess	Oxford Hip score				3				 			 	~	 	✓	 	✓	 	 	✓	✓	 	~	~	 	~	✓	 
As	Imperial Hip Score								 			 	~	 	✓	 	✓	 	 	✓	✓	 	~	~	 	~	~	 
	EQ-5D								√			 	~	 	✓	 	✓	 	 	✓	✓	 	~	~	 	~	✓	 
	AP & lateral Radiographs								√ ≤12 mos prior		~	 				 	✓	~	 		~	 					✓	~
	Low dose CT scan								⊻ ≤12 mos prior																			
	Ultra low dose CT												~		✓													
	Conmed questions								~	√	√	√	~	√	~	 	✓	 	√	✓	✓	√	~	✓	√	✓	✓	 
	Record Adverse Event(s)								 	 	~	 	~	 	~	 	✓	~	 	~	~	 	~	~	~	~	~	~

 $\checkmark$  = Cohort 1B Study Hip  $\checkmark$  = Cohort 2 Study Hip  $\checkmark$  = To be taken only if previously DXA scan not done

## Table 9. Schedule of procedures: Staggered bilateral patient recruitment from Cohort 1A into Cohort 1B

	t Study Hip hort 1A)	Pre-op	Op day	2D	6 wks	3 mos	6 mos						1 year				2 years		3 years		4 years		5 years		6 years		7 years		8,9 years		10 years	
	tralateral Second dy Hip (Cohort 1B)							Pre-op	ОР Day	2 D	6 wks	3 mos		6 mos	9 mos	1 year		2 years		3 years		4 years		5 years		6 years		7 years		8,9 years		10 years
	Re-consent for contralateral Hip							 																								
	Inclusion/exclusion							~																								
	Patient registration							 																								
	DXA Scan							√^ ≤12 mos prior																								
	Medical History							√																								
	Operative data								$\checkmark$																							
t	Treadmill gait							√					~			 							✓	 								
sme	Harris Hip Score	Ass	essm			e as pe	er	√			 	 	~	 	 	 	✓	 	✓	 			✓	 			✓	 			✓	$\checkmark$
Assessment	Oxford Hip score			Tab	le 2			 			 	 	~	 	 	 	✓	 	✓	$\checkmark$												
◄	Imperial Hip Score							√			 	 	~	 	 	 	✓	 	~	 	✓	 	✓	 								
	EQ-5D							√			 	 	~	 	 	 	✓	 	✓	$\checkmark$												
	AP & Lateral Radiographs							√ ≤12 mos prior		 									~	~			~	 							~	~
	Ultra low dose CT									 	 	 	✓	 	<	 	✓	 														
	Metal lons bloods*							 				 	✓	 		 	✓	 														
	Conmed questions							 	 	 	 	 	~	 	 	 	✓	 	~	 	✓	 	~	 	✓	 	✓	 	~	 	✓	✓
	Record Adverse Event(s)							 	~	~	~	~	~	~	~	 	~	~	~	~	✓	 	~	 	✓	 	~	 	~	 	~	~

 $\checkmark$  = First Study Hip  $\checkmark$  = Contralateral Second Hip  $\checkmark$  = To be taken only if previously DXA scan not done \*Metal ions questionnaire and bloods only taken for first 14 patients

CIP Version: Version 8 02.10.2020 IRAS ID: 213102

#### 11.1 Site Initiation and training

A site initiation visit for each participating investigation site shall be conducted and documented by the Investigation Manager at the beginning of the clinical investigation. A log shall be initiated and kept identifying names, initials, signatures, functions, and designated authorizations for the principal investigator and members of the investigation site team.

At the site initiation visit the Investigation Manager shall ensure that the principal investigator and investigation site team have received and understood the requirements and contents of all clinical trial documentation, have access to an adequate number of investigational devices, have been trained in the use of the investigational device, and are familiar with the responsibilities of the principal investigator.

#### 11.2 Patient Enrolment

#### 11.2.1 Informed Consent Process

Informed consent shall be obtained from all study participants according to ISO 14155 guidelines [44] and all applicable national regulations. Potential patients must be informed as to the purpose of the study and the potential risks and benefits known or that can be reasonably predicted or expected as described in the written consent form. The patient shall have sufficient opportunity to consider participation in the study; a patient cannot be led to believe that they are waiving their rights as a subject or the liability of the sponsor or investigator. Patients are then invited to sign and date the consent form, indicating their consent for enrolment. Once a patient has signed and dated the consent form, they are considered a participant of the study. The investigator will retain the original copy of the signed consent form in the study files. A duplicate copy shall be provided to the patient. Patients will be told they are free to withdraw at any time and they will be followed up by their healthcare team outside the study and if results throughout the 10 year study show to have an impact on patient safety, all patients will be notified and they will have the opportunity to see the consultant for further information.

The patient must sign and date the consent form in the presence of the investigator or the investigator's designee, who must sign and date the consent form in the presence of the patient.

#### 11.2.2 Screening Assessment

Check patient meets inclusion and exclusion criteria:

- DXA bone density measured t-score  $\leq$  -2.5 scan of those patients suspected to have osteopenia or osteoporosis.
- Analysis of femoral head cysts (to be undertaken at ICL)
- Calibrated X-ray used to template the implant size
- Confirmation of implant size availability from Sponsor
- If the patient is being consented for a bilateral or re-consented for the contralateral side, please check with the coordinating site (ICL) that the total number of bilateral implants inlcuded in the study will not exceed the 20% margin

## 11.3 Patient Visits

#### 11.3.1 Preoperative Procedures

Demographic information will include:

- Age at surgery
- Height (in cm) and weight (in kg), measured at the preoperative assessment visit
- Gender

Medical history will be obtained and will include:

- Significant comorbidities (HEENT, respiratory, digestive, blood/lymphatic, cardiovascular, endocrine/metabolic, musculoskeletal, integumentary, genitourinary, other)
- Primary diagnosis prompting hip arthroplasty (primary osteoarthritis, posttraumatic arthritis, avascular necrosis, developmental dysplasia)
- Previous surgeries on the affected hip (none, fracture fixation, arthroscopy, AVN treatment)
- Joint involvement status of the contralateral hip and knee, and the ipsilateral knee (currently not symptomatic, currently symptomatic, previously replaced)
- Tobacco use (Never Smoked, Past Smoker, or Current Smoker.
- Alcoholic beverage intake (Never Drinks Alcohol, Occasional or Social Drinker, Only Drinks on Weekend, or Daily Drinker)

Clinical evaluation:

- Harris Hip Score
- Patient Reported Outcome Measures:
  - UK Sites via JointPRO or paper based questionnaires (OHS, EQ5D)
  - Non UK sites Paper based questionnaires (OHS, EQ5D)
- Radiographic data: preoperative standard AP pelvis and lateral hip radiographs, performed with a calibration to allow calculation of magnification, and size of implants required.

- Gait analysis on treadmill (UK Sites only, for further information see Section 11.4)
- Preoperative CT scan (UK sites)
- Bloods (metal ion testing) and Metal ion exposure questionnaires Cohort 1A
- All Adverse Events and Serious Adverse Events must be reported.
- Concomitant medication recorded.

#### 11.3.2 Operative Procedures

Operative information for each subject will include:

- Surgical time (time from skin open to skin closure, defined as the number of minutes between start and end of the surgery)
- Surgical approach (posterior, posterolateral, anterior, anterolateral, other)
- Acetabular and femoral component sizes
- Lot and catalogue numbers of the acetabular and femoral component
- Chart stickers on the device components used are to be adhered to a page within the record.

Please refer to the Case Report Form for full details.

#### 11.3.3 Discharge Procedures

All operative complications, both intraoperative and postoperative through discharge will be collected. Any complication whether device-related, surgery related or otherwise will be collected and reported where applicable.

Post discharge information will include:

- Radiological Assessment (Section 11.6)
- Date of discharge
- Prophylactic antibiotics (yes, no)
- DVT prophylaxis (yes, no)
- Blood transfusion (yes, no; if yes specify amount in Packed RBC units)
- In case of clinical symptoms an AE form should be completed

#### **11.3.4** Follow-up Procedures – clinical visits

All patients will be seen immediately postoperatively (2days), at 6 weeks (standard postoperative visits), 6 months, 1, 2, 3, 5, 7 and 10 years following surgery. Cohort 1A will be seen additionally at 3 months, 4, 6, 8 and 9 years. Cohort 1B will be seen additionally at 3, 9 months, 4, 6, 8 and 9 years.

The following data points will be collected at the scheduled postoperative visits (see Table 2 to Table 8).

- All Adverse Events and Serious Adverse Events.
- Concomitant medication.
- Harris Hip Score (see Section 11.4).
- Patient Reported Outcome Measures (see Section 11.5)
  - UK Sites via JointPRO or paper based questionnaires (OHS, EQ5D)
  - Non UK sites Paper based questionnaires (OHS, EQ5D)
- Radiological Assessment (see Section 0)
- Gait analysis on treadmill (UK Sites only, year 1 and 5 only, for further information see Section 11.4)

In Cohort 1A the following additional investigations will be performed:

- Postoperative low or ultralow dose CT scans immediately postoperatively (2 days), 6 weeks, 3, 6, 12, 24 months to evaluate implant migration (see Section 11.7)
- Metal ion measurements in whole blood (see Section 11.8Error! Reference source not found.)

In Cohort 1B the following additional investigations will be performed:

- Postoperative ultralow dose CT scans immediately postoperatively (2 days),
   6 weeks, 3, 6, 9, 12, 24 months to evaluate implant migration. (see Section 11.7)
- Metal ion measurements in whole blood (see Section 11.8) for the fist 14 patients only

#### 11.3.5 Follow-up Procedures – remote visits

All effort will be made to ensure patients attend their follow up visits. However if a patient is unable to attend for a particular reason, they will be followed up remotely (phone, skype and/or email) so that no data is missed. If the patient has an imaging scan locally and is able to get a copy of this data, a copy should be retained and used as part of this scheduled visit point. If no imaging scan has been taken, then this will be noted down as a missed data collection point.

The following data points will be collected

- All Adverse Events and Serious Adverse Events must be reported.
- Concomitant medication recorded.
- Modified Harris Hip Score will be collected in place of Harris Hip Score
- Patient Reported Outcome Measures (see Section 11.5)
  - UK Sites via JointPRO (OHS, EQ5D, IHS) or paper based questionnaires over skype/phone/email (OHS, EQ5D)
  - Non UK sites Paper based questionnaires over skype/phone/email (OHS, EQ5D)

## 11.4 Objective Outcome Measures

A Harris Hip Score (HHS) will be completed at all postoperative visits.

A gait analysis on a treadmill (MSk Lab, Michael Uren Hub) will be performed in all UK patients who have given permission as per study consent form, pre-operatively and postoperatively at 1 and 5 years. The gait analysis will take place at the MSk Lab using an instrumented treadmill (h/p/cosmos Gaitway II S), equipped with 2 calibrated force plates. The gait parameters will be assessed for each side (prosthetic and non-operated), at a treadmill speed starting from 3/4kph and then at increasing 0.5kph increments to the maximum walking speed of the patient and will include walking on a flat surface and walking on an incline. Leg length measurements will be taken. Patient will be free to terminate the session at any time.

## 11.5 Patient Reported Outcome Measures (PROMS)

Patients will be required to complete the following questionnaires: Oxford Hip Score (OHS), EQ5D and Imperial Score (online only). Sites within the UK will be required to complete OHS, EQ5D and Imperial Score via an online web-based outcome tool JointPRO. However if for some reason patients are unable to complete these online then they will be provided a paper version of OHS and EQ5D for completion. Those patients who complete the questionnaires on paper will not be required to do the Imperial Score as this is only available on the online platform. The validated translations of the OHS and EQ5D scores will be used in the respective non-UK sites Participating sites outside the UK will complete all scores as paper-based questionnaires except for the Imperial Score as this is only available in the English language.

Patients will be required to complete the questionnaires pre-operatively and postoperatively at 6 weeks, 6,months, 1, 2, 3, 5, 7 and 10 years. Additionally cohort 1A and 1B patients will be requested to fill out the PROM questionnaires via the on-line platform at 3, 9 months (Cohort 1B only), 4, 6, 8 and 9 years.

# **11.6** Radiological Assessment

Standard AP pelvis and lateral views of the hip and/or 3D CT models will be evaluated as follows.

#### Table 10. Radiological assessment criteria

Component/ Bone	Assessment	Absolute or relative	Time point (s)	Modality
Сир	Inclination angle, °	Absolute	2 days post op	Radiograph or CT scout
Сир	Increase or decrease in inclination angle	Relative	All time points except 2d	Radiograph or CT scout
Сир	Anteversion angle, °	Absolute	2 days post op	3D CT only
Сир	Increase or decrease in anteversion angle	Relative	All time points except 2d	Radiograph or CT scout
Pelvis	Presence of acetabular radiolucency ≥2mm at the pole (Nakasone et al.)	Both	2 days post op	Radiograph
Pelvis	Increasing acetabular radiolucency in 3 zones	Both	All time points except 2d	Radiograph
Pelvis	Presence of stress shielding in 3 zones (DeLee and Charnley)	Both	All time points except 2d	Radiograph
Pelvis	Presence and size (if present) of cavities in cancellous bone in 3 zones (DeLee and Charnley)	Both	All time points except 2d	Radiograph
Head	Stem shaft angle, °	Absolute	2 days post op	Radiograph or CT scout
Head	Increase or decrease in stem shaft angle	Relative	All time points except 2d	Radiograph or CT scout
Femur	Presence of neck narrowing and percentage of narrowing (if present) in zones 1, 7, 8, 14 (De Smet et al)	Both	All time points except 2d	Radiograph or CT scout
Femur	Presence of osteophytes in zones 1, 7, 8, 14 (De Smet et al)	Both	All time points	Radiograph or CT scout
Femur	Neck notching and depth measure (if present) in zones 1, 7, 8, 14 (De Smet et al)	Both	All time points except 2d	Radiograph or CT scout
All	Any other notable abnormalities	Both	All time points	Radiograph or CT scout

In case of abnormal radiographic findings associated with clinical symptoms, an AE form should be completed.

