## 7.3.3 Safety and Efficacy Study Outcome Measures (Cohort 1A, 1B, 2)

- Implant survivorship
- Patient Reported Outcome Measures (PROMs)
- Objective clinical and functional outcomes (Harris Hip Score, Gait Analysis)
- Radiological assessment (implant orientation, osseointegration)

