#### **Radiological Assessment**

Radiological evaluation at the scheduled follow-up intervals (see flow diagram in Figure 1 to Figure 3 and Schedule of procedures in Table 2 to Table 8) will include standard anteroposterior (AP) pelvis and lateral hip radiographs, or 3D CT-series where available.

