#### Table 11. Schedule of CT scans

CT Scan	Time	Tube current (mA)	Energy (mSv)	Reason for scan	Cohort(s)
1	Pre-op	100	1.5	Hip alignment	All UK
2	2-3 days	20	0.31	Implant migration time zero	1A and 1B
3	6 weeks	20	0.31	Implant migration	1A and 1B
4	3 months	20	0.31	Implant migration	1A and 1B
5	6 months	100	1.5	Bone ongrowth & Implant migration	1A
6	6 months	20	0.31	Implant migration	1B
7	9 months	20	0.31	Implant migration	1B
8	12 months	20	0.31	Implant migration	1A and 1B
9	24 months	20	0.31	Implant migration	1A and 1B

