#### Cohort 1B

These patients will receive a total of 5 AP pelvis exposures and 5 lateral hip exposures. They will also undergo 1 low dose CT scan and 7 ultra low dose CT scans. This results in a total effective dose of approximately 7.6mSv.

#### Cohort 2

These patients will receive a total of 8 AP pelvis exposures and 8 lateral hip exposures. If at a UK site then they will additionally undergo 1 low dose CT scan. This results in a total effective dose of approximately 8mSv.

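### Table 10 reads 2-day cup anteversion on 3D CT but its later change on 2D images, and Cohort 2 has no postoperative CT to supply the 2-day value

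*Protocol*

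**What the plan says.** Implant orientation is part of a secondary endpoint (Section 8.1.3) and of an outcome measure for all three cohorts. Section 7.3.3 lists "Radiological assessment (implant orientation, osseointegration" for Cohorts 1A, 1B and 2.

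Section 11.6 introduces the reading criteria with "Standard AP pelvis and lateral views of the hip and/or 3D CT models will be evaluated as follows". Section 8.2.1 likewise names radiographs "or 3D CT-series where available". Table 10 then fixes assessment, time point and modality row by row. For cup anteversion there are two rows:

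- The absolute angle, in degrees, at 2 days, with 3D CT as the sole permitted modality.
- "Increase or decrease in anteversion angle", marked as a relative assessment, at all time points other than 2 days, with modality "Radiograph or CT scout".

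On imaging, Table 11 lists the 2-day scan ("Implant migration time zero") for Cohorts 1A and 1B only. For Cohort 2, Section 11.7.2 says "If at a UK site then they will additionally undergo 1 low dose CT scan", and Table 4 places that scan before surgery.

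**The concern.** A change in angle can be interpreted only if the reference and the later reading are made in the same way, or if the difference between methods is known. For cup anteversion, Table 10 prescribes a 3D reading at 2 days and a planar reading afterwards, and does not say which image the relative reading refers to. Two problems follow. In Cohort 2 the prescribed 2-day reading needs a scan that is not scheduled. In Cohorts 1A and 1B the scan exists, but the table directs the follow-up reading to a different modality although 3D data are available at the same visits.

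If readers follow the table literally, a difference between methods could be reported as cup movement, or could offset some real movement in this measure. If they do not, sites or readers may choose different reference images without a rule. The H1 cup is a ceramic monoblock without a metal shell, a concept the Introduction says has not been used clinically, so a consistent record of cup orientation is worth having.

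**Working it through.** No sample size, power or error rate bears on this point. The check sets Table 10 against the imaging schedules.

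**1. Modality of the angle rows in Table 10**

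| Angle | 2-day absolute value | Later change | Same modality? |
|---|---|---|---|
| Cup inclination | Radiograph or CT scout | Radiograph or CT scout | Yes |
| Cup anteversion | 3D CT exclusively | Radiograph or CT scout | No |
| Stem shaft angle | Radiograph or CT scout | Radiograph or CT scout | Yes |

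Anteversion is the only angle whose two rows differ, and 3D CT is not among the modalities for its change.

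**2. Postoperative images scheduled (Tables 2, 3, 4 and 11)**

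| Cohort | CT | AP and lateral radiographs |
|---|---|---|
| 1A | 2 days, 6 weeks, 3 and 6 months, 1 and 2 years | 2 days; 3, 5 and 10 years |
| 1B | As 1A, plus 9 months | 2 days; 3, 5 and 10 years |
| 2 | None | 2 days, 6 weeks; 1, 2, 3, 5 and 10 years |

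The exposure counts in Section 11.7.2 confirm that the tables were read correctly. With the preoperative film added, radiographs number 1 + 4 = 5 in 1A and 1B and 1 + 7 = 8 in Cohort 2, as stated there. CT scans number 1 + 6 = 7 in 1A (stated as 2 low dose and 5 ultra-low dose) and 1 + 7 = 8 in 1B (1 and 7). Cohort 2 has one, preoperative, at UK sites. The absence of a postoperative CT in Cohort 2 is therefore consistent across the protocol.

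**3. Cases affected**

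- Total 250 (Section 9.8), Cohort 1A 20 and Cohort 1B 46 (Section 8.1.1), Cohort 2 the remainder.
- Cohort 2: 250 - 20 - 46 = 184; 184/250 = 73.6%. The 2-day value as Table 10 specifies it cannot be obtained.
- Cohorts 1A and 1B: 20 + 46 = 66; 66/250 = 26.4%. The 2-day 3D value can be obtained. From 6 weeks to 2 years no radiograph is scheduled, so under Table 10 the change falls to the CT scout. At 3, 5 and 10 years it falls to the radiograph. At no follow-up visit does the listed modality match that of the 2-day value.

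Section 9.2.2 registers each hip of a bilateral patient separately, so counting cohort sizes as cases is consistent with the protocol.

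**4. Reference for the relative reading**

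Neither Table 10 nor Section 11.6 names the image against which a relative reading is made. The size of any systematic difference between 3D and planar anteversion is not given either, so no bias in degrees can be calculated from the document.

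**The case against.** The strongest reply is that the two rows serve different purposes. Only the absolute row carries a degree unit. It may be restricted to 3D CT because an absolute angle needs it, while the change is meant to be judged between serial images of like kind. AP and lateral radiographs are scheduled at 2 days in every cohort, so a comparator exists.

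Much of this stands, and it rules out several stronger readings:

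- A reader might infer that Cohort 2 has no baseline at all. It lacks only the baseline that Table 10 specifies; the 2-day radiographs could serve.
- A reader might infer that a 3D value is subtracted from a 2D value in every 1A/1B hip. No section prescribes that calculation.
- A reader might infer that cup movement would go undetected. In 1A and 1B, migration is measured separately on CT against tantalum markers to 2 years. In Cohort 2, inclination is read with the same modality list throughout, and Table 10 also lists cavities, stress shielding and other abnormalities.
- A reader might extend the point to "Increasing acetabular radiolucency in 3 zones". Both radiolucency rows are radiographic, and 2-day films are available for comparison, so the modality mismatch does not arise there.

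What the reply does not remove is the text. Table 10 limits the 2-day anteversion reading to 3D CT, so no reader is told to take one from the 2-day radiograph. No reference image is named. Even on the favourable reading, the 3D data in 1A and 1B go unused for the change.

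**Conclusion.** The point holds as an internal inconsistency in Table 10 that should be corrected. The specified 2-day anteversion value is unobtainable in 184 of 250 planned cases (73.6%). In the other 66, the change is assigned to 2D images although 3D CT is taken at 2 days and at the later CT visits to 2 years, so a change read literally may compare two methods.

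The case count assumes that Cohorts 1A and 1B recruit exactly 20 and 46. The mismatch itself needs no assumption. Its effect in degrees is unknown.

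The scope is modest: one reading within one of six secondary endpoints. Revision, the hypotheses in Section 7.2, the sample size and the tantalum-marker migration analysis do not depend on it.

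**What to change.** Amend Table 10 so that the reference and the change in cup anteversion always use the same modality, and name the 2-day image as the reference for every relative anteversion reading:

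- **Cohorts 1A and 1B, CT visits to 2 years:** 3D CT compared with the 2-day 3D CT.
- **Cohorts 1A and 1B, 3, 5 and 10 years:** radiograph compared with the 2-day radiograph. This requires adding a 2-day radiographic anteversion reading in these cohorts, because CT stops at 2 years and the 3D value alone would leave the later visits without a like-for-like reference.
- **Cohort 2:** later radiographs compared with the 2-day radiograph.
- **Reporting:** state that absolute 3D anteversion is reported for Cohorts 1A and 1B only.

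The cost is a change to the table wording and a little extra reading of images already scheduled; 2-day images already taken can be re-read. No additional scan or radiation exposure is needed. The drawback is that radiographic anteversion is less precise than CT, so change in Cohort 2, and beyond 2 years in 1A and 1B, will be measured less finely.
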